Add-on to NCT03280355

Statistical Analysis Plan for a long-term follow-up study in RCT “The Effects of Singing Training for Patients with Chronic Obstructive Pulmonary Disease (COPD)” (NCT03280355).

Document date: 06/19/2023

Title of follow-up study:

Long-term upkeep of activity, effects, and impact following pulmonary rehabilitation for COPD with either Singing for Lung Health or physical exercise training.

Study Information

In our recent multicentre RCT - *Sing-a-Lung 1.0* - comparing Singing for Lung Health (SLH) with usual-care physical exercise training (PExT) within 10 week's community-based pulmonary rehabilitation (PR) for COPD (NCT03280355), we demonstrated that SLH conferred relevant short-term improvements regarding both physiological and psychological parameters and was non-inferior to PExT.¹⁻³ Post-hoc analyses demonstrated that effect was correlated with adherence in both groups,⁴ and, moreover, suggested that SLH was associated with improved inspiratory muscle control and dyspnoea control, and that a larger proportion in SLH achieved the minimal important difference (MID) in quality of life (QoL) (measured by change in St George's Respiratory Questionnaire; SGRQ; MID = ≤ 4 units) than in physical capacity (measured by change in 6-Minute Walk Test Distance; 6MWD; MID = ≥ 30 m) (49% vs. 29%).⁵

Little is, however, known about the long-term effects of SLH including upkeep of activity, effects, and life-style changes, which is a well-known significant challenge within PR with PExT.⁶⁻⁸

Aims and hypotheses

With the present project - *Sing-a-Lung 1.1* - we will conduct a long-term follow-up study within the study cohort of *Sing-a-Lung 1.0* (n=270; SLH n=145/PExT=125) to investigate long-term upkeep of activity. Secondarily, we will investigate sustainability of effect and impact on quality of life, anxiety, depression, and dyspnoea. Furthermore, we aim to obtain deeper insight into how the study participants have integrated the tools derived from participating in either SLH or PExT.

Specifically, we aim to investigate:

Primary study outcome and hypotheses:

1. Whether level of adherence demonstrated in *Sing-a-Lung 1.0* is correlated with upkeep of activity. We hypothesise that high adherence in *Sing-a-Lung 1.0* predicts high long-term upkeep of activity after *Sing-a-Lung 1.0* and vice versa for low adherence. Moreover, we hypothesise that SLH is non-inferior to PExT in upkeeping long-term activity.
2. Whether short-term follow-up scoring values in QoL, anxiety, depression, and dyspnoea sustains at long-term follow-up. We hypothesise that SLH is non-inferior to PExT regarding sustaining of scoring and effect demonstrated in *Sing-a-Lung 1.0*.

Secondary study outcomes, and hypotheses:

- A. Whether short-term achievement of effect in QoL – defined as achievement of MID or not in SGRQ – is associated with upkeep of activity and scoring values. We hypothesise that those who achieved MID are more likely to maintain/upkeep or seek out an activity and keep up scoring values.
- B. Whether self-reported long-term level of overall physical and social activity is associated with RCT randomisation, hypothesising that SLH is non-inferior to PExT.

Whether RCT randomisation is associated with self-reported satisfaction with intervention, experienced relevance, and experienced integration of the tools obtained, hypothesising that SLH is non-inferior to PExT.

C. Whether availability of a local, structured upkeep course in physical training or a lung choir is correlated to long-term upkeep of activity, hypothesising that available local, structured offer improves likelihood of upkeep of activity. Furthermore, we hypothesise that SLH is non-inferior to PExT regarding likelihood of upkeep of activity.

Design Plan

Study type

The present study is an observational study, based on a follow-up study in the RCT cohort of *Sing-a-Lung 1.0* (n=270) (Trial registration number: NCT03280355; project title: “The Effects of Singing Training for Patients with Chronic Obstructive Pulmonary Disease (COPD)”).

Blinding

The research assistant responsible for data collection is blinded to RCT randomisation. After the analysis process, blinded results (presented as A: Level of adherence 0 compared to Level of adherence 1; and B: Treatment 0 compared to Treatment 1) will be presented to the research group, who will interpret the blinded results. Prior to unblinding of the trial results, the research group will prepare two alternative conclusions for Level of adherence and two alternative conclusions for randomisation.⁹

Study design

The present study is a long-term follow-up study of upkeep of activity and sustaining of effects across RCT study groups in *Sing-a-Lung 1.0* (SLH and PExT) using validated and specially developed questionnaires to facilitate descriptive and comparative analyses and to conduct mixed-methods inspired research equivalent to our previously published, survey-based research. The validated questionnaires cover QoL, dyspnoea, and symptoms of anxiety and depression, and are all specifically validated and used for COPD. The specially developed questionnaires were developed by PostDoc, Ph.d., [name] in close collaboration with Ph.d., Consultant in Pulmonology, [name], and discussed and settled with the additional research group members: Professor, Ph.d., Consultant in Pulmonology, [name]; Professor, D.MS.c, Consultant in Pulmonology, [name]; and Associate Professor, D.MS.c, Consultant in Pulmonology, [name].

Randomisation

Participants were randomised during the *Sing-a-Lung 1.0* RCT (Trial registration number: NCT03280355). The intervention phase of *Sing-a-Lung 1.0* took place between August 2017 and May 2019.

Sampling Plan

Existing Data

Already collected data from *Sing-a-Lung 1.0* include:

- Basic baseline characteristics: *e.g.* age, BMI, socio-demographics, smoking history, health care utilisation, exacerbations, medicine, comorbidities, and expectations towards benefits of singing.
- Baseline and short-term follow-up data related to *Sing-a-Lung 1.0* outcomes: Physical Capacity (Six-Minutes Walking Test; 6MWT), Quality of Life (St Georges' Respiratory Questionnaire; SGRQ), anxiety and depression (Hospital Anxiety and Depression Scale; HADS), dyspnoea (BORG-CR10 and Modified Medical Research Scale, mMRC), lung function (Forced Expiratory Volume in one Second; FEV1% predicted and Forced Vital Capacity; FVC% predicted), respiratory muscle strength and control (inspiratory pressure, breath counting scale, breath holding test), adherence, drop-out-rate, medicine consumption, number of COPD-related hospitalisations and exacerbations, and satisfaction with study intervention.

Sample size

RCT cohort of *Sing-a-Lung 1.0* (n=270). Participants who accept to participate will be included in the study. The following participants will be excluded from analyses: 1) Do not accept to participate, 2) Not reachable via telephone (after three attempts at different dates), 3) Deceased since *Sing-a-Lung 1.0*.

Data collection procedures

Participants from *Sing-a-Lung 1.0* have already provided written consent for a long-term follow-up contact. All participants will therefore be contacted directly by telephone by the research assistant Department of Medicine, Hospital Lillebaelt, Vejle, during February to May 2023 and asked for their consent to participate in the follow-up study. The research assistant will collect data by telephone and data will be entered directly into web-based, software survey tool and secure database, SurveyXact by Ramboll (Rambøll Management Consulting, Aarhus, Denmark)¹⁰ which will be used for survey distribution, data collection, and data storage. PostDoc, Ph.d., [name], is in charge of the overall data collection.

Data analysis procedures

In June 2023, data will be transferred from the database at SurveyXact by Ramboll to Microsoft Excel file and imported into statistical software STATA 17 (StataCorp LLC, Texas, USA). Data will be anonymised, cleaned and prepared (see section: Analysis plans/Modifications of specific variables of interest to be included in the logistic regression models) before merging with the original dataset and related 1:1 to observations from *Sing-a-Lung 1.0*. Merging and subsequent analysis process will start July 2023.

Variables

Measured variables

For the long-term follow-up study, data collection includes current smoking status, and patient-reported health care utilisation, exacerbations, and usage of COPD-related medicine since *Sing-a-Lung 1.0*. Besides, the data collection includes patient-reported knowledge on availability of local structured or unstructured offer of singing, for example a lung choir, and on availability of local structured or unstructured offer of physical training after the intervention.

Furthermore, we will collect data related to the following outcomes and variables of interest:

Study outcomes	Measure
Primary study outcome	
1. Long-term upkeep of activity	
Participation in local, structured or unstructured singing activity, for example a lung choir.Participation in local, structured or unstructured upkeep course in physical training.Participation in any other activity (physical, musical, or creative).Overall self-evaluated level of physical and social activity compared to before intervention.
Secondary study outcomes	
2. Long-term sustaining of effect - QoL, anxiety, depression, dyspnoea, etc.	
QoL: St. George's Respiratory Questionnaire (SGRQ)Anxiety and depression: (Hospital Anxiety and Depression Scale (HADS))Dyspnoea: modified Medical Research Council (mMRC) (dyspnoea scale)
3. Self-reported satisfaction with intervention, experience of relevance, and experienced integration of tools obtained during Sing-a-Lung 1.0	
Satisfaction with the interventionExperience of overall relevance of content of the interventionUse and integration of tools obtained during intervention

Analysis Plan

Statistical models

Overall

Quantitative data from validated questionnaires will be analysed using standard calculators and cut-off for minimal important differences developed for the specific tools,¹¹⁻¹⁵ In lack of a formal, absolute tool for survey research analysis,^{16,17} we will use a conventional approach to analyse quantitative and semi-quantitative data from the specially developed questionnaires. Hence, categorial data will be described with number and percentage (categorical data) and continuous data with either mean +/- standard deviation (normally distributed continuous data) or median and range (not normally distributed continuous data).

Differences in within-groups and between-groups effects will be investigated with relevant test for continuous data (independent samples, paired-samples, related-samples, and repeated-measures) and categorical data (Chi² or Fischer's test). Adjusted and unadjusted univariable and multivariable logistic regression models will be included to analyse relevant correlations. Furthermore, we will explore any potential interactions.

Baseline characteristics will be explored in the following primary and supplementary analyses: Characteristics and performance in 1) Overall total study population (baseline, short-term follow-up, and long-term follow-up), 2) Included, not accepting/not reachable, deceased, 3) Deceased (low, medium, high RCT adherence), 4) RCT randomisation (SLH, PExT).

Modifications of specific variables for analyses: 1) Adherence during RCT (ranging from 0 to 20 sessions attended; classified into three categories: zero: 0%; low: 1-49%; medium: 50-74%; high: 75-100%), 2) Intervention randomisation, 3) Sustaining of effects: QoL, anxiety, depression, dyspnoea or not (all related to minimal important difference, MID (4 units for SGRQ and 1 for HADS and mMRC), 4) Achievement of MID in RCT (SGRQ and 6MWD) or not, 5) Age categorised into quartiles, 5) FEV1% predicted categorised according to GOLD (1-4),^{6,8} 6) Baseline 6MWD categorised into quartiles, 7) Available offer of singing/physical training or not.

STROBE Statement checklist for cohort studies will be used for reporting. Statistical analyses will be performed using statistical software STATA 17 (StataCorp LLC, Texas, USA). Statistical significance will be reported as $p < 0.05$.

Ethics

Written consent for long-term follow-up contact was provided in *Sing-a-Lung 1.0* and as the long-term-follow-up study, moreover, will be solely questionnaire-based, ethical approval from The Committee on Health Research Ethics was not required. The study was approved by The Danish Act on Processing of Personal Data regarding re-accesses to the raw data of *Sing-a-Lung 1.0* in order to retrieve patients' contact information and to conduct the new questionnaire-based study of the long-term-follow-up study (REG-135-2022).

Feasibility

The long-term follow-up study will be managed and facilitated by PostDoc, Ph.d., [name]. The study will be conducted at Pulmonary Research Unit Zealand (PLUZ), Zealand University Hospital Roskilde and Naestved Hospital. Furthermore, Medical and Respiratory Department, Hospital Lillebaelt, Vejle, will participate with academic qualification and advice and will donate salary for the research assistant responsible for data collection.

Funding

Funding has been obtained from the following funding bodies: The Danish Health Foundation (DKK 200.000), The Danish Lung Foundation (DKK 100.000), Region Zealand Chiesi Pharma AB (DKK 85.000). The research assistant responsible for data collection was employed and paid by Hospital Lillebaelt.

Dissemination

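### Every singing-versus-exercise hypothesis claims non-inferiority, but the Analysis Plan specifies only difference and association tests, with no margin and no confidence-limit rule

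*SAP*

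**What the plan says.** Five statements in the SAP's Aims and hypotheses compare the randomised arms, and all five use the language of non-inferiority:

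- Item 1, upkeep of activity: "Moreover, we hypothesise that SLH is non-inferior to PExT in upkeeping long-term activity".
- Item 2, quality of life, anxiety, depression and dyspnoea: "We hypothesise that SLH is non-inferior to PExT regarding sustaining of scoring and effect demonstrated in" the parent trial.
- Hypothesis B: "Whether self-reported long-term level of overall physical and social activity is associated with RCT randomisation, hypothesising that SLH is non-inferior to PExT".
- The unlabelled paragraph after B, on satisfaction, relevance and use of tools: "experienced integration of the tools obtained, hypothesising that SLH is non-inferior to PExT".
- Hypothesis C, which largely repeats item 1: "Furthermore, we hypothesise that SLH is non-inferior to PExT regarding likelihood of upkeep of activity".

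The methods are in Analysis Plan, Statistical models, Overall. Continuous outcomes are covered by "Differences in within-groups and between-groups effects will be investigated with relevant test for continuous data" and categorical outcomes by Chi-square or Fisher tests. For models the section says: "Adjusted and unadjusted univariable and multivariable logistic regression models will be included to analyse relevant correlations". The only criterion for a conclusion is "Statistical significance will be reported as" p < 0.05; whether this is one-sided or two-sided is not stated. The Analysis Plan does not mention non-inferiority, a between-arm margin or a confidence interval.

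**The concern.** A non-inferiority claim needs a stated margin, and evidence that rules out a deficit as large as that margin. The planned tests have a different null: no difference between arms, or no association with arm. Failing to reject that null does not show that SLH is not materially worse. Rejecting it shows only that the arms differ. Hypothesis B and the paragraph after it show the mismatch within one sentence, asking about association with randomisation and answering with non-inferiority.

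At stake is the arm-comparison half of primary item 1 and every other SLH-versus-PExT comparison. With no rule written down, p ≥ 0.05 could be reported as support for the hypothesis. That result becomes more likely as numbers fall. Under Sample size, participants who refuse, cannot be reached or have died are excluded. Contact took place in February to May 2023, after an intervention phase that ran from August 2017 to May 2019. The gap is about 3.7 years (end of May 2019 to start of February 2023) to 5.8 years (start of August 2017 to end of May 2023).

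**Working it through.** **Nothing to reproduce.** The SAP gives no margin, expected upkeep rate, retention or power. The 270 (SLH 145, PExT 125) is the existing trial cohort, not a calculated sample size. The defect follows from setting the hypotheses beside the methods. The arithmetic below only shows how much it could matter.

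**Inputs from the SAP:** 145 and 125 participants; significance at p < 0.05.

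**Assumptions not in the SAP:** one binary upkeep outcome (the outcome table lists four measures); PExT upkeep of 30%, 50% or 70%; a two-sided test; true SLH deficits of 10 or 15 points; 100%, 70% or 50% of the cohort analysed; margins of 10 or 15 points.

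**Step 1: how often a real deficit is non-significant.** Let d be the deficit, p_P and p_S the upkeep proportions, n_P and n_S the arm sizes, and p̄ the pooled proportion.

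- SE0 = √[p̄(1 − p̄)(1/n_P + 1/n_S)]
- SE1 = √[p_P(1 − p_P)/n_P + p_S(1 − p_S)/n_S]
- P(non-significant) = 1 − Φ[(d − 1.96·SE0)/SE1]

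Example with the full cohort, PExT 50% and SLH 35%: p̄ = (125 × 0.50 + 145 × 0.35)/270 = 0.419, SE0 = 0.0602 and SE1 = 0.0597. Then (0.15 − 1.96 × 0.0602)/0.0597 is about 0.535, and 1 − Φ(0.535) is about 29.6%.

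P(non-significant) at PExT upkeep of 30 / 50 / 70%:

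| Analysed (SLH/PExT) | 10-point deficit | 15-point deficit |
|---|---|---|
| 145/125 (all) | 52.3 / 62.3 / 59.8% | 15.7 / 29.6 / 28.0% |
| 102/88 (70%) | 64.2 / 71.9 / 70.1% | 29.8 / 44.8 / 43.4% |
| 72/62 (50%) | 73.2 / 78.9 / 77.7% | 44.8 / 58.2 / 57.1% |

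**Step 2: precision under true equality.** SE = √[p(1 − p)(1/n_P + 1/n_S)], and the 95% CI half-width is 1.96·SE. With the full cohort and p = 0.5, SE = √[0.25 × (1/125 + 1/145)] = 0.061, a half-width of 12.0 points. Over upkeep of 30-70% the half-width is 11-12 points with all analysed, 13-14 with 70% and 16-17 with half.

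**Step 3: what a formal non-inferiority test could deliver.** Power under equality = Φ(margin/SE − 1.96).

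| Analysed | SE | 10-point margin | 15-point margin |
|---|---|---|---|
| 145/125 | 0.056-0.061 | 37-43% | 69-77% |
| 72/62 | 0.079-0.087 | 21-24% | 41-47% |

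**The case against.** Five points can be made for the plan.

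- **The SAP does contain clinical thresholds.** Under Modifications of specific variables it gives minimal important differences of 4 units for SGRQ and 1 for HADS and mMRC. These could inform margins for item 2. As written, however, they classify each patient as having sustained the effect or not, and they are not set as between-arm margins. None exists for upkeep, overall activity, satisfaction, relevance or integration of tools.
- **Results will be interpreted blind to arm**, with alternative conclusions drafted before unblinding. This reduces interpretive bias. It sets no numerical criterion for choosing the non-inferior conclusion.
- **The parent trial is reported as having shown non-inferiority.** The SAP quotes no margin from it and carries none forward, and the primary outcome here is a new one.
- **The test for continuous data is not named and sidedness is not stated**, so a non-inferiority procedure is not strictly excluded. None is specified either, and the named categorical tests and logistic models are ordinary difference or association methods.
- **The study is described as observational, and the numbers are assumed.** Both are true. The illustration covers only a binary upkeep outcome and says nothing about SGRQ, HADS, mMRC or satisfaction. The defect does not depend on it. If estimation is all that is intended, the hypotheses should say so.

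What stands is a limit on scope and a caution about the remedy. The adherence part of item 1, hypothesis A and the availability part of C do not compare the arms and are unaffected. Justifying margins for the specially developed questionnaire items may not be possible.

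**Conclusion.** The concern holds and must be fixed. All five arm-comparison hypotheses are non-inferiority claims, and the analysis specified for them cannot establish non-inferiority. Effect measure, margin and decision rule are core SAP content, so an unseen protocol does not explain the gap. The mismatch is certain from the text. Its practical size depends on upkeep, retention and margin, none of which the SAP gives. Under the stated assumptions, a 10-point SLH deficit would more often than not be non-significant even with everyone analysed. At half retention, so would a 15-point deficit at PExT upkeep of 50% or 70%.

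**What to change.** For each SLH-versus-PExT hypothesis, name the effect measure and add wording such as: *The SLH minus PExT difference will be reported with its two-sided 95% CI. Non-inferiority will be concluded only if the limit unfavourable to SLH lies inside the prespecified margin. A p-value above 0.05 is not evidence of non-inferiority.*

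- Justify each margin and put it on the scale of the reported estimate. Any use of the minimal important differences as between-arm margins for item 2 must be stated and argued.
- Fix and date the margins before the July 2023 merge and before unblinding, and disclose that they were set after data collection closed. If the merge has already taken place, any margin must be labelled post hoc.
- Where no margin can be justified, which is likely for the specially developed items, delete the non-inferiority wording and report the difference with its 95% CI.
- Reword hypothesis B and the paragraph after it so that question and hypothesis match.

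The change needs no new data and is made in the SAP text, but each margin that is kept takes real work to justify. Some comparisons will be inconclusive, as the power figures above suggest, and any margin will carry the disclosed limitation on its timing.

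### Hypothesis A uses the short-term SGRQ change only as MID achieved or not; if upkeep varies smoothly with that change, about 36% of the exposure information is lost at the one documented responder share

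*SAP*

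**What the plan says.** Hypothesis A (SAP, Secondary study outcomes, and hypotheses) takes short-term effect on quality of life as its exposure, "defined as achievement of MID or not in SGRQ", and asks whether it "is associated with upkeep of activity and scoring values". The expected direction is stated in terms of participants who reached the MID.

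The Analysis Plan repeats the coding. Item 4 of the variable modifications reads "Achievement of MID in RCT (SGRQ and 6MWD) or not", and item 3 gives the thresholds as "4 units for SGRQ and 1 for HADS and mMRC". The section on data analysis procedures describes this list as the preparation of variables for the logistic regression models, so the yes/no variable is a model input and not just a table label. No model with the SGRQ change as a continuous exposure is named.

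The full-scale data exist: under Existing Data the SAP lists "Baseline and short-term follow-up data related to" the RCT outcomes, SGRQ among them.

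The cohort is fixed ("n=270; SLH n=145/PExT=125"). Under Sample size, "Participants who accept to participate will be included in the study"; refusal, failed contact and death reduce the number further. The SAP gives no expected number analysed, upkeep rate, effect size, SD or power.

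**The concern.** Cutting a measured change at 4 units treats everyone on one side alike. A participant who improved by 3.9 units is grouped with one who worsened by 15, and one who improved by 4 with one who improved by 25. If the chance of keeping up activity rises steadily with the gain in quality of life, those differences carry information that the test cannot use.

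Recruitment cannot make up the loss. At most 270 people are available, about four to six years after the intervention phase, so the coding of the exposure is one of the few means left to protect precision. Results are reported against a 0.05 threshold. A real association could therefore be missed, and the null result read as showing that a gain in quality of life does not predict upkeep.

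**Working it through.** The SAP states no power or precision figure for hypothesis A, so there is none to reproduce. The check asks what the cut costs under stated assumptions.

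**Inputs from the SAP.** The exposure is binary at 4 SGRQ units. The share reaching the SGRQ MID is 49%, given in Study Information for the SLH arm only; the 29% beside it is for 6MWD. The cohort is at most 270. The significance level is 0.05, sidedness not stated.

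**Assumptions.** Roughly normal SGRQ change; log-odds of upkeep linear in the change; two-sided test; pooled responder share p between 30% and 49%; 50% upkeep; analysed n and odds ratio per SD as shown below.

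**Step 1: information kept by the cut.** For a normal exposure split so that a share p falls on one side, the retained fraction is E = φ(z_p)² / [p(1−p)].

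- p = 0.49: φ = 0.3988, so E = 0.1591 / 0.2499 = 0.636. About 36% is lost.
- p = 0.40: E = 0.622. About 38% is lost.
- p = 0.30: φ = 0.3477, so E = 0.1209 / 0.2100 = 0.576. About 42% is lost.

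With 140 analysed, the cut at p = 0.49 is worth about 0.636 × 140 = 89 participants on the full scale.

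**Step 2: power.** If the full-scale test has power P, the cut test has power Φ[(1.960 + z_P)·√E − 1.960]. For P = 80% and p = 0.49: (1.960 + 0.842) × 0.798 − 1.960 ≈ 0.275, and Φ ≈ 60.8%.

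| Full-scale power | Cut, p = 0.49 | Loss (points) | Cut, p = 0.30 | Loss (points) |
|---|---|---|---|---|
| 50% | 34.6% | 15.4 | 31.8% | 18.2 |
| 80% | 60.8% | 19.2 | 56.6% | 23.4 |
| 90% | 73.4% | 16.6 | 69.1% | 20.9 |
| 95% | 82.0% | 13.0 | 78.1% | 16.9 |
| 97.5% | 87.8% | 9.7 | 84.5% | 13.0 |

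**Step 3: simulation at fixed n** (50% upkeep, odds ratio 1.6 per SD; full scale against cut).

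| n | p = 0.49 | p = 0.30 |
|---|---|---|
| 100 | 63% vs 45% | 64% vs 41% |
| 140 | 76% vs 56% | 78% vs 55% |
| 180 | 87% vs 70% | 86% vs 64% |

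The small differences between the two full-scale figures in a row are simulation error. Over n = 100 to 180 and odds ratios 1.4 to 1.8, the loss is about 10 to 24 points.

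**Step 4: where the size changes.**

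- Low power (n = 100, odds ratio 1.3): losses of 7.7 (p = 0.49) and 9.5 points (p = 0.30).
- Very high power (n = 270, odds ratio 1.7): losses of 6.3 and 10.3 points.
- Heavy-tailed change scores (t with 5 degrees of freedom; n = 100 to 270, odds ratio 1.3 to 1.7): losses of 9 to 27 points.
- A true step at the MID (60% against 40% upkeep, p = 0.49): the cut wins, 67.6% vs 47.8% at n = 150 and 90.6% vs 72.6% at n = 270.

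**The case against.** The strongest reply is that the plan answers the question it asks. The hypothesis is worded about people who reached the MID, the threshold was fixed in advance and not chosen from the data, and a responder contrast is easy to read. This stands, and it is why the MID contrast should stay. A reader might infer that the test is invalid or that the binary variable should be removed; the documents support neither.

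Second, the size is conditional. The SAP gives no upkeep rate, effect size, SD or follow-up number, and only one responder share, for one arm. It also lists several measures of upkeep instead of a single binary outcome at 50%. A reader might take the power loss as a property of this study. It is not: it belongs to the assumed scenarios. Nothing in the SAP argues for a step at 4 units, but nothing argues for linearity either.

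Third, the SAP plans tests for continuous data in general, and comparing the SGRQ change between those who did and did not keep up activity would fit that wording. It is not tied to hypothesis A, so it mitigates only partly.

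Three extensions are tempting but unsupported. Item 4 also names 6MWD, but hypothesis A names only SGRQ and no model using the 6MWD variable is specified. Measurement error near the threshold might seem to weaken the cut further, but error also attenuates a continuous slope, and it was not modelled here. The calculations concern upkeep only and say nothing about the part of hypothesis A on long-term scores.

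**Conclusion.** The point holds as an efficiency weakness in a secondary hypothesis. The SAP enters the short-term SGRQ change only as MID achieved or not, while holding the full scores for a cohort that cannot be enlarged.

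Under a roughly normal change and a near-linear log-odds relation, the information loss is about 36% at the documented 49% share and up to about 42% at an assumed 30%. The corresponding power loss is about 10 to 24 points for n = 100 to 180, odds ratios 1.4 to 1.8 per SD and 50% upkeep. It is smaller where power is very low or very high, and the advantage reverses if upkeep steps at the MID. The binary test remains valid for the hypothesis as worded. What it supports poorly is a general statement that a gain in quality of life does not predict upkeep.

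**What to change.** For hypothesis A, pre-specify a logistic model of upkeep on the continuous short-term SGRQ change. Code the change so that positive means improvement, report the odds ratio per 4-unit improvement (one MID) with its 95% CI, and check linearity, for example with a three-knot spline. State that any conclusion that quality-of-life gain does or does not predict upkeep rests on this model. Keep the MID achieved/not contrast beside it to answer the hypothesis as worded. No change is asked for on 6MWD.

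The cost is SAP wording and one additional analysis on data already held. The headline becomes less familiar than a responder contrast, and the continuous model has less power if the true relation is a step at the MID; the retained contrast covers that case. The SAP is dated June 2023, with merging and analysis planned from July 2023. If the merged data have already been analysed, the added model should be labelled as not pre-specified.

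### Time from course end to interview varies from about 45 to about 67 months, but it is not among the variables listed for the logistic models or for description

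*SAP*

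**What the plan says.** **Dates.** Under Randomisation, the SAP says the intervention phase "took place between August 2017 and May 2019". Under Data collection procedures, participants are contacted by telephone "during February to May 2023". Study Information describes the two modalities as delivered "within 10 week's community-based pulmonary rehabilitation". The SAP states no length of follow-up.

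**Models.** The Overall paragraph under Statistical models says: "Adjusted and unadjusted univariable and multivariable logistic regression models will be included to analyse relevant correlations". No model is written out with its covariates. Data analysis procedures points to a section on "Modifications of specific variables of interest to be included in the logistic regression models". The matching list opens with "Modifications of specific variables for analyses: 1) Adherence during RCT" and closes with "7) Available offer of singing/physical training or not". In between stand randomisation, sustaining of effects, MID achievement in the RCT, age quartiles, GOLD class of FEV1 and baseline 6MWD quartiles. Time since intervention, course date and calendar period are not there. They are also not named under Existing Data, under Measured variables, or among the characteristics to be described.

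**Questions.** The first primary hypothesis is that "high adherence in *Sing-a-Lung 1.0* predicts high long-term upkeep of activity". The second question is whether short-term scores hold at long-term follow-up. Sustained effect is tied to fixed MIDs: 4 units for SGRQ, and 1 for HADS and mMRC.

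**The concern.** Courses were spread over nearly two years, while the interviews fall in one window of four calendar months. Participants are therefore asked about upkeep, and scored for sustained effect, after quite different intervals. Both outcomes concern persistence, and the chance of still being active, or of staying within a fixed MID of an earlier score, plausibly changes with time.

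This matters most for the questions that do not rest on randomisation: adherence and upkeep (primary), short-term MID achievement and upkeep or scores (secondary A), and local availability and upkeep (secondary C). If early and late courses differed in attendance, in response or in the local offers that followed, part of an association credited to adherence, response or availability could reflect elapsed time. The listed adjustment variables (age, FEV1, 6MWD) do not capture this.

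**Working it through.** The SAP gives no follow-up length, so there is no planned figure to reproduce. The check is calendar arithmetic on its dates.

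**Inputs from the SAP.** Intervention phase August 2017 to May 2019; interviews February to May 2023; course length 10 weeks. I take the first course to start in August 2017 and the last to end in May 2019.

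**Shortest interval.** Last course end to first interviews, May 2019 to February 2023: (2023 − 2019) × 12 + (2 − 5) = 45 months. By exact day within those months it is 44.1 to 46.0.

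**Longest interval.** A course starting between 1 and 31 August 2017 ends 10 weeks later, between 10 October and 9 November 2017.
- October 2017 to May 2023: 6 × 12 + (5 − 10) = 67 months.
- November 2017 to May 2023: 6 × 12 + (5 − 11) = 66 months.
- By exact day: 65.7 to 67.6 months.

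**Spread.** 66 − 45 = 21 and 67 − 45 = 22 months. The ratio of longest to shortest is 66/45 = 1.47 to 67/45 = 1.49.

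**How far this could move one participant's classification.** The SAP gives no rate of decline and no SD of change, so what follows is illustration. Assume SGRQ worsens by d = 0.5 to 2 units a year, that change has SD 10 to 14, and that not sustained means worsening by more than 4 units from the short-term score. The SAP gives the size of the MID but does not spell out that last rule.
- Shift in mean score over 22 months: 0.5 × 22/12 = 0.9 to 2 × 22/12 = 3.7 units.
- P(not sustained) = 1 − Φ((4 − d·t)/SD). From t = 45/12 to t = 67/12 years it rises by 2.6 points (d = 0.5, SD 14) to 12.6 points (d = 2, SD 10).

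This compares the longest-followed with the shortest-followed participant. It is not an estimate of bias.

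**What confounding would depend on.** The relevant quantity is the difference in mean follow-up between the groups compared, which the SAP does not give. If that difference were 3 months around the middle of the range (56 to 59 months), the same formula gives about 0.4 points (d = 0.5, SD 14) to 1.7 points (d = 2, SD 10).

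**What the arm comparison could gain.** If course ends were spread evenly over 21 months and calls over 4, the SD of follow-up would be √(21²/12 + 4²/12) = 6.2 months, about 0.5 year. The share of SGRQ-change variance explained is (d × 0.5)²/SD²: 0.03% (d = 0.5, SD 14) to 1.0% (d = 2, SD 10).

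**The case against.** The strongest reply is that this is a suggestion for one more covariate and exposes no contradiction in the plan. Nothing in the SAP links adherence, MID response or local availability to calendar time, so the confounding path is plausible but not shown. The direction is also uncertain: the deceased are excluded, and if more have died after longer follow-up, those remaining may be the healthier ones. All of this stands, and it limits the point to a candidate confounder of unknown size and sign.

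A reader might infer more in four ways, none of which the document supports.

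- **That time enters no model.** The SAP writes out no full covariate set, and the list concerns recoded variables, from which an unmodified continuous covariate could be absent. What can be said is that time is not among the variables listed for the models. The general mention of relevant correlations and potential interactions does not prespecify it either.
- **That follow-up reaches 69 months, with a 24-month spread worth a whole SGRQ MID.** August 2017 to May 2023 is 69 months, but that counts from the start of the phase. From course end the maximum is about 67, and the assumed shift stays below 4 units.
- **That misclassification of about 3 to 14 percentage points is the bias.** That figure contrasts two extreme participants, uses the 69-month maximum and rests on assumed decline rates.
- **That the arm comparison loses worthwhile precision.** The explained variance is at most about 1% on these assumptions, and in logistic models a prognostic covariate does not generally shrink the standard error of the log odds ratio.

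**Conclusion.** The point holds as a modest improvement. On the SAP's own dates, follow-up from course end differs by about 21 to 22 months between participants (about 45 to about 67 months), and elapsed time is in neither the list tied to the logistic models nor the planned descriptions. The range assumes that courses filled the intervention phase from its first to its last month.

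For SLH against PExT, randomisation should roughly balance elapsed time, apart from selective death and non-response, so adjustment adds little. For adherence, MID achievement and availability nothing balances it, and there it belongs in the adjusted models. The size of any bias cannot be derived, because the SAP gives neither the distribution of course dates by group nor any relation of time to upkeep or scores.

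**What to change.** Derive, for each participant, the months from the end of their own course to the interview date. Report the distribution by arm and by adherence level. Prespecify it as a continuous covariate in the adjusted upkeep and sustained-effect models, chiefly those for adherence, MID achievement and availability.

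The cost is one derived variable and one degree of freedom per model. It requires individual course and interview dates. The SAP does not say that these are held, so this should be confirmed first. The SAP is dated 19 June 2023 and places merging and analysis from July 2023, so on its own timetable the change could be made before analysis.
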